
**[F]CTT1057: A promising investigational PSMA-PET radiotracer**

Most experts in the field agree, the future of PSMA-based PET imaging will be with F-labeled tracers because of the practical advances: F has a longer half-life than Ga, which enables the tracers to be distributed to PET centers without a cyclotron and to be easily handled in clinical routine. In addition, the higher positron decay branching of F (96.9%) versus Ga (87.7%), together with the shorter positron range of F, account to the higher PET imaging resolution achieved with F-labeled radiopharmaceuticals (Conti and Eriksson 2016). [F]CTT1057 is a promising novel PSMA-targeting F-labeled PET imaging agent. Unlike most other PSMA agents labelled with either Ga or F (e.g. [Ga]Ga-PSMA-11, [F]PSMA1007, [F]DCFPyL) which share a urea backbone, [F]CTT1057 is based on a phosphoramidate scaffold that [REDACTED] binds to PSMA with high nanomolar affinity, which may account for a higher and prolonged tumor uptake (Behr et al 2019). Together with the higher resolution of PET/CT images when using a F-labelled PSMA agent, it would therefore favor the identification of smaller lesions, and consequently, also at earlier stages of the disease.

A Phase-I study in 20 PCa patients (n=5 primary staging, n=15 metastatic-castration resistant prostate cancer (mCRPC)) (Behr et al 2019) has shown an acceptable safety profile, without any radiotracer-related adverse reactions. The biodistribution of [F]CTT1057 in humans is similar to that of other PSMA-targeted agents, and exposure rates of [F]CTT1057 are also similar to those of the urea-based PET compounds, with the advantageous exception of lower exposure to kidneys and salivary glands. Preliminary evidence of diagnostic performance of [F]CTT1057 PET in detecting and localizing PSMA-positive tumors was provided from the n=5 primary staging patients using pathology as SoT. Abnormal [F]CTT1057 PET uptake corresponding to the pathology-proven cancer was shown in 4 of the 5 subjects. The only subject who did not show PET uptake in the primary tumor had the lowest PSA in the cohort. The Phase-I study also demonstrated that metastatic lesions are detected with higher sensitivity on [F]CTT1057 imaging than on conventional imaging (Behr et al 2019). Another smaller study showed that the image quality on [F]CTT1057 PET imaging was qualitatively similar to that obtained on [Ga]Ga-PSMA-11 PET (Behr et al 2017).

Further details on [F]CTT1057 can be found in the Investigator's Brochure (IB).

## 1.2 Purpose

The purpose of this study is to evaluate the diagnostic performance of [F]CTT1057 as a PET imaging agent for detection and localization of PSMA positive tumors using histopathology as SoT. Tissue specimens from both the primary tumor and PLN dissected during surgery from patients with newly-diagnosed high-risk PCa will be used for the histopathology assessments.

## 2 Objectives and endpoints

**Table 2-1 Objectives and related endpoints**

Objective(s)	Endpoint(s)
Primary objective(s)	Endpoint(s) for primary objective(s)

 
Evaluate the patient-level sensitivity of [F]CTT1057
 
	
 
Sensitivity of [F]CTT1057 PET imaging, considering PSMA positive patients as those who show at least one pathological
 

Objective(s)	Endpoint(s)
	[  F]CTT1057 uptake either in the primary tumor and/or metastatic PLN regions, with anatomically localized correspondence with the SoT. See Section 2.1 for Primary Estimand.

 
Evaluate the region-level specificity of [F]CTT1057
 
	
 
Specificity of [F]CTT1057 PET imaging, defined as proportion of PLN regions that test negative for lymph nodes on [F]CTT1057 among those that are lymph node negative on the SoT. See Section 2.1 for Primary Estimand.
 

Secondary objective(s)	Endpoint(s) for secondary objective(s)

 
Evaluate the patient-level specificity of [F]CTT1057
 
	
 
Specificity of [F]CTT1057 PET imaging, considering PSMA negative patients as those who do not show any pathological [F]CTT1057 uptake either in the primary tumor or PLNs and will be confirmed not having primary tumor or metastatic PLNs with the SoT
 

 
Evaluate the patient-level positive predictive value of [F]CTT1057
 
	
 
Proportion of patients who are both [F]CTT1057 and SoT positive (true positives (TP) among those who test positive on [F]CTT1057 (TP+ false positives(FP))
 

 
Evaluate the patient-level negative predictive value of [F]CTT1057
 
	
 
Proportion of patients who are both [F]CTT1057 and SoT negative (true negatives (TN)) among those who test negative on [F]CTT1057 (TN+ false negatives (FN))
 


 
Evaluate the patient-level accuracy of [F]CTT1057
 
	
 
Proportion of patients that are SoT and [F]CTT1057 positive (TP) and negative (TN) among all patients in EFF (TP+TN+FP+FN)
 

 
Evaluate the region-level sensitivity of [F]CTT1057 for patients excluding micro-metastasis
 
	
 
Sensitivity of [F]CTT1057 PET imaging in the PLN region, excluding from the analysis those lymph nodes showing metastasis <2mm (micro-metastasis)
 

 
Evaluate the region-level sensitivity of [F]CTT1057
 
	
 
Proportion of PLN regions that test positive on both [F]CTT1057 and SoT (TP) among those that are SoT positive (TP+FN)
 

 
Evaluate the region-level positive predictive value of [F]CTT1057
 
	
 
Proportion of PLN regions that are SoT and [F]CTT1057 positive (TP) among those regions that test positive on [F]CTT1057 (TP+FP)
 

 
Evaluate the region-level negative predictive value of [F]CTT1057
 
	
 
Proportion of PLN regions that are SoT and [F]CTT1057 negative (TN) among those regions that test negative on [F]CTT1057 (TN+FN)
 

 
Evaluate the region-level accuracy of [F]CTT1057
 
	
 
Proportion of PLN regions that are SoT and [F]CTT1057 positive (TP) and negative (TN) among all PLN regions assessed [F]CTT1057 (TP+TN+FP+FN)
 

 
Detection of distant metastasis in PS patients
 
	
 
Number of distant metastasis (extra-PLN, visceral or skeletal) identified at PET/CT scan per patient, and percentage of patients with at least one distant metastatic lesion identified by PET/CT scan
 


 
Characterize the safety and tolerability of [F]CTT1057
 
	
 
Incidence of AEs. Treatment emergent adverse event (TEAE) rate within 14 days of administration
 

 
[F]CTT1057 scan inter-reader variability
 
	
 
Inter-reader agreement of [F]CTT1057 images
 

Objective(s)	Endpoint(s)

 
[F]CTT1057 scan intra-reader variability
 
	
 
Intra-reader agreement of [F]CTT1057 images
 

 
To further assess [F]CTT1057 pharmacokinetics in humans in subset of approximately 10 patients
 
	
 
Summary statistics of [F]CTT1057 pharmacokinetic parameters (i.e. Cmax, Tmax, AUClast, AUCinf, T1/2, Vz and CL from blood radioactivity data; quantification of urinary excretion of [F]CTT1057 from urine data)
 

## 2.1 Primary estimands

The primary clinical question of interest is: Does [F]CTT1057 target PSMA expressing PCa cells, allowing to obtain adequate [F]CTT1057 PET/CT images to detect and localize PSMA positivity using histopathology as SoT?

The justification for the primary estimand is that we wish to assess the diagnostic performance of [F]CTT1057 PET in detecting and localizing PSMA positivity. For this reason, newly-diagnosed high risk PCa patients will undergo a [F]CTT1057 PET/CT scan within 6 weeks before surgery (but not sooner than 48 hours after the completion of the [F]CTT1057 PET/CT scan), and results of the [F]CTT1057 PET/CT scans will be compared against the histopathology results (SoT) in the dissected tissue specimens (primary tumor and PLN), both at a patient and region level.

The primary estimands are described by the following attributes:

Primary estimand 1:

- Population: Untreated high risk PCa patients according to D'Amico classification (Stage  $\geq$  T2c or PSA level  $>20$ ng/ml or Gleason score  $\geq 8$ ) (D'Amico et al 1998), who are scheduled or planned RP and lymph node resection. Further details about the population are provided in Section 5.
- Variables: Proportion of patients that test positive on both [F]CTT1057 and SoT (TP) among those that are SoT positive ( TP + FN), considering PSMA positive patients are those who show at least one pathological [F]CTT1057 uptake either in the primary tumor and/or metastatic PLN, with anatomically localized correspondence with the SoT.

3. Treatment (investigational imaging agent) of interest: [F]CTT1057 injected as a single intravenous dose of approximately 370 MBq and subsequent PET/CT scan. Further details about the investigational imaging agent are provided in [Section 6](#).
4. Handling of remaining intercurrent events:
  - Patients who received the investigational imaging agent [F]CTT1057 but did not undergo/complete the PET/CT scan for any reasons (e.g. consent withdrawal, PET camera failures, etc.), will be excluded from the primary analysis. Details on how to handle intercurrent events are provided in [Section 12.4.3](#).
5. Summary measure: Estimate of proportion of patients that test positive on both [F]CTT1057 and SoT (TP) among those that are SoT positive (TP + FN), considering PSMA positive patients are those who show at least one pathological [F]CTT1057 uptake either in the primary tumor and/or metastatic PLN, with anatomically localized correspondence with the SoT, along with its 95% CI. Further details on how the summary measure will be tested are provided in [Section 12.4.2](#).

#### Primary estimand 2:

1. Population: the same as the primary estimand 1
2. Variables: Proportion of PLN regions that test negative on both [F]CTT1057 and SoT (TN) among those PLN region that test negative on the SoT (TN + FP), considering PSMA negative PLN regions those that do not show any pathological [F]CTT1057 uptake within the region.
3. Treatment (investigational imaging agent) of interest: the same as the primary estimand 1
4. Handling of remaining of intercurrent events: the same as the primary estimand 1
5. Summary measure: Estimate of the proportion of PLN regions that test negative on both [F]CTT1057 and SoT (TN) among those PLN region that test negative on the SoT (TN + FP), considering PSMA PLN negative regions those that do not show any pathological [F]CTT1057 uptake within the region, along with its 95% CI. Further details on how the summary measure will be tested are provided in [Section 12.4.2](#).

## 2.2 Secondary estimands

Not applicable

## 3 Study design

[figure not shown]
This is a multi-center, single-arm, open-label prospective study to evaluate the diagnostic performance of [F]CTT1057 as a PET imaging agent for detection and localization of PSMA positive tumors, using histopathology as SoT. Tissue specimens from both the primary tumor and PLN dissected during surgery from patients with newly-diagnosed high-risk PCa will be used for the histopathology assessments.

Approximately 195 participants will be enrolled to ensure that at least 156 participants are evaluable for co-primary endpoints. Surgery will be performed up to 6 weeks after [F]CTT1057 PET/CT but not sooner than 48 hours after the completion of the [F]CTT1057 PET/CT scan (in order to limit the potential confounding factors related to the effects of surgery

for the assessment of [F]CTT1057 PET/CT safety) for pathology assessment of the tissue specimens.

[figure not shown]
The co-primary endpoints of patient-level sensitivity and region-level specificity will be assessed by comparing the central reading results of the [F]CTT1057 PET/CT scan (see Section 4.1 and Section 8.3.1 for central read details and Section 6.4 for blinding details) to the histopathology results in the dissected tissue specimens, i.e. both the primary tumor and the dissected PLN (Maurer et al 2016, Woythal et al 2018, Kuten et al 2020).

Pathology will be assessed by the local pathologists as per SoC. Pathologists will be blinded to the PET data. For anatomical localization, a sextant anatomic template for the prostate and a left/right template for the PLN will be used (see appendix Section 16.2). Pathology results should be available within 2 weeks after surgery.

See Figure 3-1 for study design schema.

Figure 3-1 Study Design

### Screening Period

Written informed consent form (ICF) must be obtained prior to any screening procedures. The participant must be registered in the Interactive Response Technology (IRT) for screening and [F]CTT1057 requested. All procedures described in the Assessment Schedule as per Table 8-1 must be carried out, prioritizing laboratory assessments to allow time to obtain the results at least 14 days prior the planned PET imaging day (Day 1). The participants will be

assessed for eligibility before they will undergo a [ $^{18}\text{F}$ ]CTT1057 PET/CT scan. Eligibility must then be confirmed at the latest on Day -14. The screening period should last up to 28 days.

#### **[ $^{18}\text{F}$ ]CTT1057 PET imaging day:**

[ $^{18}\text{F}$ ]CTT1057 PET imaging will be performed using a standard integrated PET/CT system. The following steps to take place during this day are described in [Section 8.3.1](#).

In the PK subset of approximately 10 participants at the same site, several blood and urine samples as well as additional ECG assessments for safety will be done at the pre-specified time points on PET imaging day.

#### **Safety Check**

All treated participants will be contacted by phone within 24 to 72 hours following the scan in order to capture potential occurring Adverse Events.

#### **Safety Follow-up**

Participants will come back to the hospital 14 days after the PET/CT scan day, for a safety visit including vital signs, lab and urine analysis. For participants undergoing surgery prior to planned safety visit, these safety follow-up assessments will need to be performed before the surgery but not sooner than 48 hours after the PET/CT scan.

#### **Additional Follow-up**

Surgery (RP/ePLND) will be scheduled for all participants as planned per SoC on a date that must not be sooner than 48 hours after the completion of the [ $^{18}\text{F}$ ]CTT1057 PET/CT scan, and no later than 6 weeks after completion of the [ $^{18}\text{F}$ ]CTT1057 PET/CT scan. Final histopathology results have to be obtained within 2 weeks after surgery.

## **4 Rationale**

### **4.1 Rationale for study design**

In this study, a single-dose of the investigational PET imaging radiopharmaceutical [ $^{18}\text{F}$ ]CTT1057 will be administered intravenously, in an open-label single-arm design.

The most commonly used measures for evaluating the diagnostic performance of a new imaging modality are sensitivity and specificity. Histopathology of the tumor samples is considered as the SoT to assess the diagnostic performance of PET tracers targeting PSMA ([Maurer et al 2016](#), [Woythal et al 2018](#), [Kuten et al 2020](#)). In PS patients, both the primary tumor and the metastatic lymph nodes (LN) are expressing PSMA, which is the target for [ $^{18}\text{F}$ ]CTT1057 binding. Within a period of up to 6 weeks after completion of the [ $^{18}\text{F}$ ]CTT1057 PET/CT scan, patients will undergo surgery as per their standard of care treatment plan, consisting of RP and ePLND, as per the European Association of Urology (EAU) guidelines for Prostate Cancer 2020 (refer to [Section 16.1](#)).

In addition to the prostate dissection, a minimum of 12 PLN per patient will be dissected in order to have enough numbers of PLN in total for the calculation of the co-primary endpoints and the diagnostic performance yielding secondary endpoints.

Local pathologists with experience in PCa who will be blinded to the [F]CTT1057 PET/CT results will then assess the tissue specimens as per SoC. For the anatomical correspondence with PET/CT images, a sextant template will be used for the prostate (Kuten et al 2020). For the PLN, an anatomical side approach left/right will be used, since the borders of dissection are not usually very clear neither for the surgeon nor for the pathologist.

A central read of the PET/CT scan will be performed at a Contract Research Organization (CRO) by a total of three independent nuclear medicine physicians or radiologists experienced in reading oncology PET, who will be blinded to patient data, including the clinical condition of the patient, results of histopathology/biopsy, and results of conventional imaging. Patients and regions will be graded on a two-point scale by each reader (0 = negative; 1 = positive). The results from each of the 3 readers will be individually compared to the SoT to generate per-reader performance. An individual PET reader will be considered successful if he/she meets predefined thresholds for both co-primary endpoints, and at least two of three readers should be successful for overall study positive. PET results will be compared to histopathology results, and anatomically localized positive lesions in both PET and histopathology will be considered “TP” for sensitivity and specificity calculations as the primary endpoints of the study.

[figure not shown]
Regions defined for this study are prostate region (comprising prostate bed/prostate gland and any local invasion of the urinary bladder, rectum or seminal vesicles), PLN region, extra-PLN region, skeletal region and visceral region.

The criteria to be applied for PET positivity is the following:

- A patient will be judged as positive if at least one lesion in any region is visually positive.
- A region will be judged as positive if at least one lesion in the region is visually positive.
- Visually PET positive lymph nodes will be considered greater than blood pool (adjacent or mediastinal blood pool).
- PET positive bone lesions will be considered greater than physiologic bone marrow.
- PET positive prostate, prostate bed and visceral lesions will be considered greater than physiologic background activity of the involvement organ or anatomic site, as previously described (Ceci et al 2015, Eiber et al 2015, Fendler et al 2019).

Only prostate region and PLN will be used as regions for comparison to the SoT and co-primary endpoint calculations.

Consistency of the PET/CT scan interpretation both between different readers and within readers is an important issue in medical imaging, as it affects portability of results between institutions and may affect patient care. The degree of inter- and intra-reader variability in the qualitative assessment of [F]CTT1057 PET/CT images will be assessed as a secondary endpoint to ensure consistency of interpretation and hence reliable diagnosis, which has pivotal role in the patient management.

[REDACTED]. Further details on the questionnaire and procedure are provided in [Section 3](#).

In order to reproduce as much as possible the real clinical context, this [F]CTT1057 PET/CT scan will be read by a local nuclear medicine physician or radiologist with expertise in reading oncology PET/CT scans who will not be blinded to patient data. See also [Section 6.4](#) and [Section 8.3](#) for blinding and reading details.

The co-primary endpoints will not be assessed in those patients who, as a consequence of a change in treatment will not be considered suitable for surgery. These patients will remain in the study for the assessment of some secondary [REDACTED]

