[F]CTT1057 PET/CT images will also be read by an independent local nuclear medical physician or radiologist with expertise in reading oncology PET/CT scans, who will not be participating in the central read of images. The report from this local reader will be provided to the treating physician/ Clinical Study Investigator to complete [REDACTED] before the participant undergoes surgery. The criteria to be applied for PET positivity are detailed in [Section 4.1](#).

[F]CTT1057 PET/CT imaging data to be documented in eCRF will include the outcome of the assessment, i.e. if negative or positive for PCa tumor or metastases, region(s) and location of the lesions as well as their characteristics.

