#### 12.4.5 Sensitivity analyses for primary endpoint/estimand

Not applicable

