A large variability in sensitivity of PSMA-PET in the primary staging setting has been reported. Two recent systematic reviews of [Ga]PSMA PET /CT diagnostic accuracy focused on the PS population using pathology as SoT, sensitivity of 33–99% across studies has been reported (Corfield et al 2018), as well as pooled sensitivity and specificity ranges of 23-100% and 67-100% respectively (Petersen and Zacho 2020). Recent preliminary data on the diagnostic efficacy of F-18-rhPSMA-7.3 PET imaging in PS patients compared to histopathology (n=56) reported a 95% CI low bound patient level sensitivity of 54.4% (81.3 (95% CI-54.4-96.0) (Maurer et al 2020). CT and MRI are the standard of care imaging procedures for measuring tumors at baseline and lesions selected for response assessment as per RECIST criteria 1.1 (Eisenhauer et al 2009). A meta-analysis on the diagnostic accuracy of CT and MRI in the staging of pelvic lymph nodes in patients with PCa reported a pooled sensitivity of 0.42 (95% CI 0.26-0.56) for CT, and of 0.39 (95% CI 0.22-0.56) for MRI (Hövels et al 2008). A study evaluating the diagnostic value of [Ga]PSMA PET versus CT and MRI for lymph node staging in 130 consecutive patients who got RP and PLN dissection after PET/Magnetic Resonance (MR) (n=95) and PET/CT (n=35) and who had tumor specimens available for reanalysis to correlate with PET reported a sensitivity of 43.9% (95% CI 28.5-60.3) and 85.4% specificity (95% CI 76.3-92.0) for morphological imaging alone (CT and MRI) (Maurer et al 2016).

Taking all the above into consideration, an overall patient-level sensitivity of 50% and a region level specificity of 70% will be considered as unacceptably low. Hence, the sample size calculation will be performed based on the null and alternative hypotheses as follows.

- Patient-level sensitivity

For patient-level sensitivity, the null hypothesis H0: patient-level sensitivity p0 = 0.50 will be tested against the alternative hypothesis H1: p1>0.50, assuming a sensitivity of 0.63 under the alternative hypothesis, approximately 156 patients with primary tumor and/or metastatic lymph nodes would achieve 90% statistical power to detect a change in sensitivity of 0.13 using a one-sided binomial test at a target significance level of 2.5%. Taking into account 20% dropout rate, 195 patients can ensure the 90% statistical power.

- Region-level specificity

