For region-level specificity, the null hypothesis  $H_0$ : region-level specificity  $p_0 = 0.70$  will be tested against the alternative hypothesis  $H_1$ :  $p_1 > 0.70$ . Assuming a specificity of 0.85 under the alternative hypothesis, approximately 123 patients (which includes 37 patients with PLN based on 30% prevalence) would achieve 90% statistical power to detect a change in specificity of 0.15 using a one-sided binomial test at a target significance level of 2.5 %. Taking into account 20% dropout rate, 154 patients can ensure the 90% statistical power. The lower bounds of the 95% CI for specificity should be greater than 0.70 to be considered success.

The lower bound of the 95% CI for sensitivity should be greater than 0.50 and the lower bound of the 95% CI for specificity should be greater than 0.70 for the study to be considered a success.

A total sample size of 195 patients can ensure 90% statistical power for patient-level sensitivity and 99% statistical power for region-level specificity resulting in an overall study statistical power of at least 89.1% ( $0.9 \times 0.99$ ).

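### Men whose surgery is cancelled after PET leave the co-primary analysis unexamined; if cancellation tracks the pelvic-node PET result, specificity is overstated against the 0.70 bar

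*Protocol*

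**What the plan says.** - **Information flow.** The local reader is not blinded to patient data (Protocol 4.1, 6.4). Protocol 8.3.1 states: "The report from this local reader will be provided to the treating physician/ Clinical Study Investigator", and this happens before the participant has surgery.
- **Exclusion.** Under Protocol 4.1 the co-primary endpoints are not assessed in men who "as a consequence of a change in treatment will not be considered suitable for surgery"; they stay in the study for some other endpoints. The efficacy analysis set (EFF) requires both an evaluable scan and histopathology (Protocol 12.1, SAP 2.2).
- **Target population.** Both primary estimands concern men scheduled or planned for prostatectomy and node resection (Protocol 2.1, SAP 1.2.1), not only men operated on.
- **Handling.** The only intercurrent event is a dosed participant without a completed scan (Protocol 12.4.3, SAP 2.5.3). Missing data are not imputed (Protocol 12.4.4, SAP 2.5.4). The entry for sensitivity analyses is "Not applicable" in Protocol 12.4.5, and the same in SAP 2.5.5. The supplementary logistic models use the EFF as well (SAP 2.5.6).
- **Room for loss.** Protocol 12.8.1 says: "Taking into account 20% dropout rate, 195 patients can ensure the 90% statistical power". That allows for 195 − 156 = 39 non-evaluable men.
- **Safeguard.** Protocol 4.5 says that a changed management plan will not rest on the investigational scan alone but will be confirmed by standard-of-care procedures.

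**The concern.** Whether a man is verified by histopathology can depend on what his scan showed. Suppose node-negative men with PLN uptake are operated on less often than node-negative men without it. False-positive regions then leave the denominator more often than true-negative ones, and the observed specificity exceeds the specificity in the estimand population. The bar is fixed at 0.70, so the bias works towards success on a co-primary endpoint.

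The rule that two of three readers must succeed does not protect against this, because all three are scored on the same verified men. Nor do the supplementary models, which are fitted only to men who were verified. For patient-level sensitivity the effect runs the other way: losing true-positive men makes success harder.

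**Working it through.** **Inputs from the documents.** Null values: "an overall patient-level sensitivity of 50% and a region level specificity of 70% will be considered as unacceptably low". Test: "using a one-sided binomial test at a target significance level of 2.5" percent, equivalent to an exact (Clopper-Pearson) 95% lower bound above 0.70 (SAP 2.5.2, 5.4.1). Planning: "Assuming a specificity of 0.85 under the alternative hypothesis", with "approximately 123 patients (which includes 37 patients with PLN based on 30% prevalence". Evaluable men: 156.

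**Assumed, because the documents give no figure.** c is the share of false-positive node-negative men left unverified, and d the share of true-negative men left unverified.

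**Step 1: the plan's own figure.** 123 − 37 = 86 node-negative men. The exact test passes at 69 or more of 86; error at 0.70 is 2.2% and power at 0.85 is 91.4%, consistent with the stated 90%. 123/0.8 = 154 (rounded up), as stated. At 156 evaluable men there are 156 × 0.70 ≈ 109 node-negative men; the test passes at 86 or more, with error 2.4%.

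**Step 2: effect of selective loss.** With true specificity s = 0.70:

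apparent specificity = s(1−d) / [s(1−d) + (1−s)(1−c)]

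verified n = 109 × [s(1−d) + (1−s)(1−c)]

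Example, c = 10%, d = 0: 0.70/(0.70 + 0.27) = 0.722; n = 109 × 0.97 ≈ 106; pass at 84 or more; probability 6.1%.

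| c | d | Apparent specificity | Verified n | Pass at | Error per reader |
|---|---|---|---|---|---|
| 0 | 0 | 0.700 | 109 | 86 | 2.4% |
| 5% | 0 | 0.711 | 107 | 85 | 3.3% |
| 10% | 0 | 0.722 | 106 | 84 | 6.1% |
| 20% | 0 | 0.745 | 102 | 81 | 15.1% |
| 20% | 5% | 0.735 | 99 | 79 | 9.3% |
| 20% | 10% | 0.724 | 95 | 76 | 5.8% |
| 20% | 20% | 0.700 | 87 | 70 | 1.9% |

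The 10% row is a loss of about 3 men (109 × 0.30 × 0.10 = 3.3). The last row shows that loss unrelated to the PLN call does no harm to the error rate.

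**Step 3: local and central reads differ.** Cancellation can follow only the local read; scoring uses the central reads. Assume that both have specificity 0.70 and agree with kappa 0.6 among node-negative men. Chance agreement is 0.3² + 0.7² = 0.58, observed agreement 0.58 + 0.6 × 0.42 = 0.832, and both-positive (0.832 − 0.40)/2 = 0.216. So 0.216/0.30 = 72% of central false positives and 0.084/0.70 = 12% of central true negatives are locally positive. Cancelling 20% of locally positive men gives c = 14.4%, d = 2.4% and error 7.6%; cancelling 10% gives 4.1%.

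**Step 4: tipping points.** Add unverified men as false positives.

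- 86/109: lower bound 0.7004. One added man, 86/110: 0.693, a fail.
- 93/109 (0.853): lower bound 0.773. Nine added, 93/118: 0.703, still a pass. Ten added, 93/119: 0.696, a fail.

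**Step 5: sensitivity.** Losing 10% of true-positive men moves 0.63 to 0.567/(0.567 + 0.37) = 0.605 and cuts power from 90% to 69% (n = 146).

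**The case against.** The strongest reply is that no passage says men with PLN uptake are diverted from surgery. Protocol 4.1 speaks of a change in treatment without naming its cause. Where the documents link imaging to management, they mean distant disease (Protocol 4.5) or nodal sites outside the dissection template (Protocol 1.1). Surgery with extended node dissection is an entry condition, and Protocol 3 schedules it for all participants. If cancellation is driven only by findings unrelated to the PLN call among node-negative men, there is no inflation. This stands, and it makes the point conditional. It does not settle it: the local report does reach the treating physician, and the Protocol 4.5 safeguard reduces selective loss without excluding it.

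A second reply is that planned outputs already expose the loss: discontinuations with reasons (SAP 2.3.1), analysis-set counts (SAP 2.2), and baseline tables for both the full analysis set and the EFF (SAP 2.3.2). This is partly right, and it would be wrong to infer that nothing planned would reveal the loss. These outputs show how many men are missing, but not the central PLN calls of the men lost, which is what decides the direction of bias. Some text is also redacted, so exploratory reporting on unoperated men cannot be excluded; the sections on co-primary sensitivity analyses are visible and empty.

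Third, the figures are for specificity in one reader, whereas study success needs both endpoints in at least two readers. That is correct, and the figures should be read that way.

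**Conclusion.** The gap is real: exclusion after a reported scan is built into the design, the analysed men differ from the estimand population, and no planned analysis tests whether that matters. The size is unknown. The error rises to 3.3%, 6.1% or 15.1% only if 5%, 10% or 20% of false positives and no true negatives are lost, the true specificity is 0.70, 109 node-negative men are available before loss, and local and central reads agree. It is smaller with imperfect agreement or offsetting loss, and about 2% if cancellation is unrelated to the PLN call among node-negative men.

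A reader might infer that the 0.70 test has lost its error rate, or that the error is of the order of 17% to 28%. The documents do not support either. Such figures need 20% to 30% selective loss, and they also hold 109 as the verified number after the loss. No document gives a diversion rate, and Protocol 4.5 points towards a small one. The justified conclusion is that a cheap check should be pre-specified, not that the specificity result is invalid.

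**What to change.** List surgery not performed after PET as an intercurrent event in Protocol 12.4.3 and SAP 2.5.3. Replace the empty entries in Protocol 12.4.5 and SAP 2.5.5 with the following, for each central reader:

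1. A cross-tabulation of the central PLN and prostate calls by histopathology obtained or not, with the reason, for all dosed participants with an evaluable scan.
2. A verification-corrected specificity stratified on the central PLN call (Begg-Greenes), labelled as a sensitivity analysis that assumes verification depends only on that call.
3. A tipping point: the number of unverified PLN-positive men who would have to be node-negative for the lower bound to fall to 0.70 or below.

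Multi-variable weighting is not recommended; it would be fragile with at most a few dozen unverified men. The primary test and both thresholds stay as they are.

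The cost is SAP text and a few tables. Scans go to central read without a condition on surgery (Protocol 6.4, 8.3.1), so no new patients or reads should be needed. The downside is that the corrected specificity may be less favourable.
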